8.3.6. Objective Sleep and Physical Activity Parameters (Actigraphy)

Actigraphy is the process of measuring physical movement of an individual over time to assess the degree of motor activities and will provide an objective measure of sleep prior to treatment. The actigraphy device is a small, motion biosensor that is worn on the non-dominant wrist to monitor daily activity and sleep patterns. Participants are asked to wear the device continuously throughout the screening and DB Treatment phases of the study. Actigraphy recorded movements can be used to estimate sleep parameters with specialized algorithms. Actigraphy has been validated for the estimation of nighttime sleep parameters across age groups (Martin 2011) and psychiatric conditions (Ancoli-Israel 2003, Baandrup 2015). Subjective and objective sleep assessment may assess different constructs of sleep and may not have a high correlation (Smith 2018).

Participants will be instructed to wear an actigraphy device on their non-dominant wrist from screening to End of DB Treatment phase or Early Withdrawal. Participants should wear it during the day and night except when bathing. If a participant is not able to tolerate wearing the actigraphy device (either at night or during the day), the participant may continue in the study and the use of

the actigraphy device may be discontinued. Movements during the day and night will be captured. Daytime physical activity may be analyzed. The primary purpose of actigraphy in this study is to have an objective measure of sleep and physical activity parameters to complement the SDI, CMAI-C, NPI-12 and NPI-C.

The parameters collected will include but are not limited to the following:

- sleep onset latency
- total sleep time
- wake after sleep onset (WASO)
- sleep efficiency
- physical activity.

8.3.7. Off-body touchless sensors

This procedure will be implemented in the study as an optional assessment and only if available. The off-body touchless sensors will be used in a subset of participants who agree to use them during the study. The sensor(s) will be placed in the participants home and used from screening to end of the study.

The off-body touchless sensor is a radio wave based touchless sensor and machine learning platform for health analytics. The off-body touchless sensor operates by transmitting and receiving low power radio signals that reflect off of the surroundings and return back to the device. The power of these signals is 1,000 times lower than what a typical Wi-Fi device transmits, and existing research has not shown these power levels to impact health in any way. The transmissions have been designed to be in compliance with the Federal Communications Commission (FCC) regulations governing indoor ultra-wideband (UWB) systems (Part 15.517).

The sensor(s) will be installed in the participant bedroom and optionally, in an additional living area of the participant, to passively collect mobility and sleep metrics from screening to end of the study. The sleep staging from this touchless sensor has shown good agreement (Cohen's $\kappa = 0.7$) of electroencephalogram (EEG)-based sleep stages (Zhao 2017). The off-body touchless sensor provides additional data not available from wrist-worn actigraphy including the predicted sleep stages. These complementary measures may prove useful in understanding sleep patterns (Zhao 2017).

The device operates by transmitting and receiving low power radio waves that reflect off nearby objects, pets and people and return back to the device. Data collected by the off-body touchless sensor will be encrypted and transmitted via Wi-Fi to a secure vendor's file server.

The participant will need to wear a small accelerometer (for approximately 14 days during the screening period). The layout of the room and the side of the bed in which the participant sleeps, will be entered into the vendor's companion app by study mobile personnel. This information will allow the vendor to create an algorithmic filter that recognizes motion patterns from the consented

individual extracted by the device. These machine learning algorithms run on the collected data to produce exploratory clinical endpoints (ie, mobility or sleep metrics). No identifiable information is collected at any point by the vendor as all data is labeled by a randomly generated identifier that is unique for the duration of the study.

As shown in Figure 2, the radio waves are first combined with information from the participant worn accelerometer, and configuration information (ie, participant side of bed and bedroom layout) using a machine learning model that produces a participant specific filter. This filter is used by the vendor's platform to remove irrelevant information, and the participant specific relevant information is then processed by the platform to produce the data specific to the participant.

8.4. Adverse Events, Serious Adverse Events, and Other Safety Reporting

Timely, accurate, and complete reporting and analysis of safety information, including AEs, SAEs, and PQCs, from clinical studies are crucial for the protection of participants, investigators, and the sponsor, and are mandated by regulatory agencies worldwide. The sponsor has established Standard Operating Procedures in conformity with regulatory requirements worldwide to ensure appropriate reporting of safety information; all clinical studies conducted by the sponsor or its affiliates will be conducted in accordance with those procedures.

Adverse events will be reported by the participant (or, when appropriate, by a caregiver, surrogate, or the participant's legally acceptable representative) for the duration of the study.

Further details on AEs, SAEs, and PQCs can be found in Section 10.4, Appendix 4: Adverse Events, Serious Adverse Events, Product Quality Complaints, and Other Safety Reporting: Definitions and Procedures for Recording, Evaluating, Follow-up, and Reporting.

8.4.1. Time Period and Frequency for Collecting Adverse Event and Serious Adverse Event Information

All Adverse Events

All AEs and special reporting situations, whether serious or non-serious, will be reported from the time a signed and dated ICF is obtained until completion of the participant's last study-related procedure, which may include contact for follow-up of safety.

Serious Adverse Events

All SAEs, as well as PQCs, occurring during the study must be reported to the appropriate sponsor contact person by study site personnel within 24 hours of their knowledge of the event.

Serious adverse events, including those spontaneously reported to the investigator within 30 days after the last dose of study intervention, must be reported. The sponsor will evaluate any safety information that is spontaneously reported by an investigator beyond the time frame specified in the protocol.

Information regarding SAEs will be transmitted to the sponsor using the Serious Adverse Event Form, which must be completed and signed by a physician from the study site, and transmitted to the sponsor within 24 hours. The initial and follow-up reports of an SAE should be made by facsimile (fax). Telephone reporting should be the exception and the reporter should be asked to complete the appropriate form(s) first.

8.4.2. Method of Detecting Adverse Events and Serious Adverse Events

Care will be taken not to introduce bias when detecting AEs or SAEs. Open-ended and nonleading verbal questioning of the participant is the preferred method to inquire about AE occurrence, except AESIs. For AESIs investigators are instructed to inquire about the occurrence of such events during the collection of AEs at each visit.

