Study Procedure								
Off-body touchless sensors (in a subset of the participants)	Continuous ^q							
Ongoing Participant								
Review								
Concomitant therapy	Continuous							
Adverse events	Continuous							

Note: AD=Alzheimer's Disease, ADAS-Cog-14=Alzheimer's Disease Assessment Scale Cognitive subscale, 14 items, CDR=Clinical Dementia Rating, CMAI-C= Cohen-Mansfield Agitation Inventory community version, C-SSRS= Columbia Suicide Severity Rating Scale, DB=double-blind, DSM-5=Diagnostic and Statistical Manual of Mental Disorders, ECG=electrocardiogram, EW=early withdrawal, FU=follow-up, GDSI = Geriatric Depression Scale, informant version, HIS=Hachinski Ischemic Scale, ICF=informed consent form, IPA=International Psychogeriatric Association, MMSE=Mini-Mental State Examination, NPI=Neuropsychiatric Inventory, PK=pharmacokinetics, PWC=Physician Withdrawal Checklist, SCR=screening, SDI=Sleep Disorder Inventory

Footnotes

- a. Must be signed before first study-related activity.
- b. Minimum criteria for the availability of documentation supporting the eligibility criteria are described in Source Documentation in Appendix 3, Regulatory, Ethical, and Study Oversight Considerations. Check clinical status again before first dose of study medication.
- c. Supine vital signs should be measured after 5 minutes of rest in a supine position. If blood sampling or vital sign measurement is scheduled for the same time point as ECG recording, the procedures should be performed in the following order: ECG(s), vital signs, blood draws.

- d. If possible, participants should be fasted (ie, no food or beverages [except water]) for at least 8 hours before blood is drawn for clinical chemistry, insulin, hemoglobin A1c [HbA1c], and hematology.
- e. Participants and study partners will receive brief psychosocial therapy (BPST) during screening. A number of sessions will be scheduled during the screening period and should be completed at Visit 2 (baseline).
- f. For the remote contact at Visit 3 (Day 8), approximately 7 days after Visit 2, participants and their study partners will be contacted remotely (ie, by telephone or videoconference) and queried for AEs, overall seltorexant dosing compliance and tolerance, any changes in concomitant therapies, and medication diary completion.

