Visit 2 will occur on Day 1 (baseline). Study restrictions and any changes in inclusion/exclusion criteria will be reviewed, and an alcohol breath test and urine drug screen performed. Other assessments will be completed as per the SoA at this and subsequent visits.

Upon completion of Visit 2 assessments, eligible participants will be randomized and receive the study medication to take home for the double-blind treatment period, including instructions and a medication diary. Participants and study partners will be reminded about the use of the actigraphy device.

Visit 3

Approximately 7 days after Visit 2 (baseline), the participant and their study partner will be contacted remotely (ie, by telephone or videoconference) and queried for AEs that may have occurred between the last visit and remote follow up, and overall study drug dosing compliance and tolerance, and medication diary completion.

Visit 4

Visit 4 will take place at the end of Week 2 of the double-blind treatment period.

Upon completion of Visit 4 assessments, participants and study partners will be reminded about the use of the actigraphy device.

Visit 5

Visit 5 will be at the end of Week 4 of the double-blind period and is preferred to be done on-site; if done remotely, the NPI-C should be conducted by videoconference if possible (with audio-recording)

Visit 6

Visit 6 will be at the end of Week 6 of the double-blind treatment period or at the time of early withdrawal from study treatment. At Visit 6, participants and study partners will return the actigraphy device.

All participants who discontinue study drug in the DB treatment phase, will have an Early Withdrawal visit (Visit 6 in the Schedule of Activities [SoA]), preferably the day after the last dose. After completion of this visit, the participant enters the follow-up phase. All participants who

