5.1. Inclusion Criteria

Each potential participant must satisfy all of the following criteria to be enrolled in the study:

Age

1. 55 to 85 years of age, inclusive.

Type of Participant and Disease Characteristic

2. Criterion modified per Amendment 1

2.1. Participant has received a diagnosis of probable AD (DSM-5) with the following characteristics at screening:

- CDR global score ≥ 1
- MMSE total score of 10 to 24 (inclusive)
- 3. Participant meets the criteria of a syndrome diagnosis of agitation based on International Psychogeriatric Association (IPA) consensus clinical and research definition of agitation in cognitive disorders for at least 2 weeks before screening (see Appendix 6 for the criteria).
- 4. Participant meets the criteria of NPI-12 A/A domain score ≥ 4 with frequency score ≥ 2 at screening and baseline with no more than 35% of improvement in NPI-12 A/A domain score from the screening to baseline assessments.
- 5. Participant is medically stable on the basis of clinical laboratory tests performed at screening. If the results of the serum chemistry panel, hematology, or urinalysis are outside the normal reference ranges, the participant may be included at the discretion of the investigator if he/she judges the abnormalities or deviations from normal not to be clinically significant or to be appropriate and reasonable for the population under study. This determination must be recorded in the participant's source documents and initialed by the investigator.
- 6. Participant must be medically stable on the basis of the following: physical examination, neurological examination, vital signs (including blood pressure), and 12-lead ECG performed at screening and baseline. If there are any abnormalities that are not specified in the inclusion and exclusion criteria, their clinical significance must be determined by the investigator and recorded in the participant's source documents and initialed by the investigator.
- 7. Participant is considered eligible according to the following COVID-19 screening criteria:
 - Has no history of possible or confirmed COVID-19 infection at screening and within 14 days prior to screening. Possible or confirmed COVID-19 diagnosis may be based on:

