 - Symptomatology at least 1 of the following main symptoms: cough, dyspnoea, thoracic pain, acute anosmia or dysgeusia without clear aetiology OR have at least 2 of the following symptoms: fever, muscle pain, fatigue, rhinitis, sore throat, headache, anorexia, watery diarrhoea without clear aetiology, acute mental confusion, acute falls without clear aetiology OR worsening of chronic respiratory infections (COPD, asthma, chronic cough...)
 - Radiology suggestive clinical presentation AND compatible thorax CT, even if laboratory COVID-19 antigen test is negative
 - Laboratory test positive COVID-19 antigen test
 - Signs or symptoms suggestive of active COVID-19 upon medical history and/or physical examination.
 - Recent (within 14 days) close contact with a person with possible or confirmed COVID-19.

CONFIDENTIAL – FOIA Exemptions Apply in U.S.

Weight

8. Body mass index (BMI) within the range $18-40 \text{ kg/m}^2$ (inclusive).

Sex and Contraceptive/Barrier Requirements

- 9. Female participants must be postmenopausal before study entry (amenorrhea for at least 12 months).
- 10. Male participant:
 - who is heterosexually active with a woman of childbearing potential must agree to use a double-barrier (a combination of male condom with either cap, diaphragm, or sponge with spermicide) method of birth control and his female partner must use a highly effective method of contraception
 - must agree not to donate sperm during the study and for 3 months after receiving the last dose of study agent
 - who is sexually active with a woman who is pregnant must use a condom
 - must not plan to father a child while enrolled in this study or within 3 months after the last dose of study intervention.

Informed Consent

- 11. A participant in the study must have a designated study partner who will accompany the participant to each study visit. A study partner can be a relative, friend or caretaker indicated by the participant, who is at least 18 years old, who may or may not live with the participant, who has at least 8 hours of contact with the participant each week (ie, 4 days a week for at least 2 hours per day), and who is available at each visit. As judged by the investigator, study partners should have adequate literacy to participate and be judged to have high likelihood of completing the study with the participant.

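### Section 8.4.2 prefers questioning the participant, who has dementia, to find adverse events and does not tell sites to ask the study partner, so who is asked may vary and events may be missed

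*Protocol*

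**What the plan says.** **Who is questioned.** Protocol Section 8.4.2 sets the method: "Open-ended and nonleading verbal questioning of the participant is the preferred method to inquire about AE occurrence, except AESIs". On AESIs it adds: "For AESIs investigators are instructed to inquire about the occurrence of such events during the collection of AEs at each visit". Section 8.4.6 repeats that instruction. Neither section says who answers the AESI questions, and 8.4.2 does not mention the study partner.

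**Who may report.** Section 8.4 begins: "Adverse events will be reported by the participant (or, when appropriate, by a caregiver, surrogate", and goes on to include the legally acceptable representative. It does not say when reporting by someone else is appropriate.

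**The population and the partner.** Inclusion criterion 2.1 in Section 5.1 requires "MMSE total score of 10 to 24 (inclusive") together with a CDR global score of at least 1. Under criterion 11, each participant "must have a designated study partner who will accompany the participant to each study visit".

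**The Day 8 contact.** Footnote f of the schedule (Section 1.3) says that "participants and their study partners will be contacted remotely (ie, by telephone or videoconference) and queried for AEs". The Visit 3 text in Section 4.1 says the same.

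**The concern.** This is the first study of seltorexant in Alzheimer's disease, and safety and tolerability are among its stated aims. The sentence that tells sites how to find ordinary adverse events points them to the person whose recall is impaired. An informant is in the building, but the section gives sites no instruction to ask that person.

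Elsewhere the protocol does not rely on the participant alone. The NPI-12 is a caregiver interview (8.1.1), the NPI-C interviews both people (8.1.2), the SDI is rated by the caregiver (8.1.3), and the GDSI is the informant version of a self-report scale (8.1.5). The partner oversees or assists with dosing and the diary (6.4). Routine adverse event questioning at the on-site visits is the exception.

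Two things are at stake. Whether the partner is asked may depend on the site, which adds variation unrelated to treatment. And if events are missed at a similar rate in both arms, absolute differences in the adverse event tables (SAP Section 5.6.2) shrink toward zero.

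**Working it through.** **1. The instructions side by side**

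| Place in the protocol | Contacts covered | Respondent |
|---|---|---|
| 8.4 | whole study | participant; others if appropriate (undefined) |
| 8.4.2, events other than AESIs | whole study | participant, as the preferred method |
| 8.4.2 and 8.4.6, AESIs | each visit | none named |
| 4.1, Visit 3 | Day 8 | participant and partner |
| 1.3, adverse event query row | marked with footnote f at Days 8 and 29; the footnote text describes Day 8 only | participant and partner |
| 1.3, same row | no entry at Days 15, 43 and 57 | Sections 8.4 and 8.4.2 govern |
| 1.3, adverse events row | continuous | none named |

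Only the Day 8 text clearly directs that both people be asked. Day 29 carries the footnote mark, but the footnote does not describe that visit. For Days 15, 43 and 57 the only rules are 8.4, which permits a caregiver to report, and 8.4.2, which prefers questioning the participant. Permission to report is weaker than an instruction to ask.

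**2. Recall periods.** Taking the contacts in order: 15 − 8 = 7 days before Day 15, and 29 − 15 = 43 − 29 = 57 − 43 = 14 days before Days 29, 43 and 57. At Day 15 the participant therefore has about one week to recall since the joint Day 8 query. At Days 43 and 57 it is two weeks.

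**3. What depends on the open question.** The AESIs in 8.4.6 are somnolence, cataplexy, sleep paralysis, complex sleep-related behaviours, falls and motor vehicle accidents. Sections 2.1 and 2.3 list three identified adverse drug reactions: somnolence, abnormal dreams and sleep paralysis. Abnormal dreams is not an AESI, so it gets no directed question and relies on the open question to the participant. For AESIs the question is directed, but who answers is left open.

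**4. Size.** The documents give no adverse event rate, no detection sensitivity and no figure for agreement between participant and partner, so there is nothing to reproduce. The following shows scale only, on assumed values, with 86 / 2 = 43 per arm.

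*Difference between arms.* Assume true incidences of 20% and 5% and a share *s* of affected participants detected, equal in both arms. Expected counts are 43 × 0.20 × *s* and 43 × 0.05 × *s*; the difference in percentage points is 15 × *s*.

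| *s* | Expected counts | Difference |
|---|---|---|
| 1.0 | 8.6 vs 2.2 | 15 points |
| 0.8 | 6.9 vs 1.7 | 12 points |
| 0.6 | 5.2 vs 1.3 | 9 points |
| 0.4 | 3.4 vs 0.9 | 6 points |

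The ratio between arms stays at 4 to 1 throughout; only the absolute difference shrinks.

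*Seeing an event at all.* The chance of at least one detected case in an arm is 1 − (1 − *p* × *s*)^43. For *p* = 5% it is 0.89, 0.86, 0.81 and 0.66 at *s* = 1.0, 0.9, 0.75 and 0.5. For *p* = 10% it is 0.99, 0.98, 0.96 and 0.89.

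Every one of these results depends on an assumed *s*. The loss from the present wording is the gap between *s* under that wording and *s* when both people are asked, and the documents fix neither.

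**The case against.** A reader might infer that adverse events *will* be under-detected, or that Days 15, 43 and 57 are participant-only by design. The documents support neither.

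- A preferred method is not an exclusive one. Section 8.4 allows a caregiver to report, and with an MMSE of 10 to 24 that condition is readily met. Section 2.3 expects the partner to give further feedback on treatment issues, and the partner is present anyway. This defeats the claim of certain loss. It does not supply an instruction to ask.
- Footnote f describes one remote contact and does not say that the partner is left out elsewhere. That is correct: the text leaves the respondent open at other visits, so variation between sites is a possibility, not a stated plan.
- Many of the night-time and next-day effects a partner might notice are AESIs, which are asked about at each visit and are exempt from the open-question preference. This narrows the concern considerably. What remains is that no AESI respondent is named and that abnormal dreams is outside the list.
- The partner is not necessarily the better witness. Criterion 11 does not require the partner to live with the participant and asks for only 8 hours of contact a week. This stands, and it is a reason to ask both people rather than substitute one for the other.
- Other routes do not depend on recall. Examinations, weight, vital signs, ECG and laboratory tests are done at Day 43, and Section 8.2 requires clinically relevant changes to be recorded as adverse events. These help with measurable abnormalities, less with symptoms.

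**Conclusion.** The point holds as a weakness in how adverse events are elicited, and correcting it is a cheap improvement. Section 8.4.2 prefers the participant as respondent in a population with dementia, leaves the AESI respondent unnamed, and does not match the joint query at Day 8. Events may therefore be under-detected, and practice may differ between sites.

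The size is unknown. The illustrative figures rest on assumed incidences and detection shares, with detection equal in the two arms. They do not estimate what this trial would lose, nor how much asking the partner would recover. The conclusion rests on the text alone: the partner is already at every visit, the protocol already has both people queried at Day 8, and nothing requires the same at Days 15, 43 and 57.

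**What to change.** Amend Section 8.4.2, and the matching sentence in 8.4, to say that at every visit and contact the open-ended adverse event question and the AESI questions are put to both the participant and the study partner, and that an event reported by either is recorded. The open-ended, non-leading form can stay. This extends to all contacts what footnote f and Section 4.1 already do at Day 8.

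The cost is protocol wording, a few minutes per visit and some extra minor reports. No new visits are needed. Partners with as little as 8 hours of contact a week will not see every event, so the change reduces the gap without closing it.
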